### **12.2 Data Monitoring Committee**

The data monitoring committee will include one study investigator paired with one scientist who is not an investigator in this trial.

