## **9 ADVERSE EVENT REPORTING**

### **9.1 Adverse Event**

For the purpose of this protocol, the following definitions and reporting requirements will apply:

An adverse event (AE) is any untoward medical occurrence associated with the performance of a study procedure in a clinical investigation patient.

AEs may include:

- Symptoms described by the patient
- Clinically significant changes in the patient's physical exam or other signs observed by the Investigator or medical staff

Definition of a Procedure-related AE:

A procedure-related AE is an AE occurring during a clinical study that is considered by the Investigator or the Medical Monitor (or designee) to be related to a research procedure (i.e., related to the fact that a patient is undergoing a procedure in the study). For example, a procedure-related AE may be an event related to a medical procedure required by the protocol (a single blood draw or an injury from an Aerobic-surge performed in the normal course of this study).

Only serious procedure-related adverse events will be recorded.

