### **9.3 Evaluation of Adverse Events/Serious Adverse Events**

SAEs will be assessed by the PI. Only SAEs determined by the Investigator to be possibly related or related to study procedures will be recorded. Any study-procedure-related or possibly-related SAEs ongoing after the Screening/Baseline visit will be followed until resolution.

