#### **9.3.1 Causality Assessment**

For each SAE the Investigator must determine whether, based on available evidence, there is a reasonable possibility that the study procedure caused the event. Causal relationship will be classified according to the following criteria:

- Not Related: There is no suspicion of a causal relationship between the procedure and the AE.
- Unlikely Related: There is no evidence for a causal relationship between the procedure and the AE; however, such a relationship cannot be ruled out.
- Possibly Related: There is some evidence supporting the possibility of a causal relationship between the procedure and the AE.
- Related: There is strong evidence that there is a causal relationship between the procedure and the AE.

A causality assessment must be provided for each SAE recorded even if there is only limited information at the time.

Upon receipt of follow-up information, the Investigator may change his/her assessment of causality and amend the SAE report accordingly.

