## 9.4 Reporting Serious Study-Procedure-Related Adverse Events

### 9.4.1 Initial Reporting of Serious Study-Procedure-Related Adverse Events

Study-procedure-related or possibly related SAEs should be recorded using appropriate medical terminology. When recording, it is preferable to provide a diagnosis. In the absence of a diagnosis, each sign and symptom should be captured as a unique SAE. Sufficient information should be sought to assist the Investigator both in determining the diagnosis and in making a causality assessment.

The necessity and time requirements for reporting of study-procedure-related or possibly related SAEs to the Sponsor or its designee and/or regulatory agencies are as follows:

- All SAEs related or possibly related to study procedures must be reported to the IRB or designee within 24 hours of the Investigator's first knowledge of the event.
- A completed Clinical Study SAE Report Form containing a detailed written description of the event along with available supporting documents (e.g., discharge summary, autopsy report, diagnostic test results, etc.) should be provided by fax or e-mail to the following address:

Safety Reporting [name], BSN, CPN
[contact] E-mail: [contact]

- Additional information that is not available at the time the initial SAE Report Form was completed, must be promptly reviewed and provided to the IRB within 48 hours of receipt. Full supporting documentation should be solicited by the investigative site even if the SAE occurred at another institution. Such documentation may include copies of relevant patient/hospital records, discharge summaries, laboratory/test results or autopsy reports.
- If, at any time after the patient has completed participation in the study (as defined in Section 0), the Investigator or study staff becomes aware of an SAE that they suspect is related to the study procedures (see Section 9.3.1), then the event and any known details must be reported promptly to the Sponsor or its designee, following the reporting instructions in Section 9.4.3.

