#### **12.4.5 Study or Site Termination**

If the NIH or its designee, the Investigator, or regulatory authorities discover any conditions during the study that indicate that the study or study site should be terminated, this action may be taken after appropriate consultation between the Sponsor or its designee and the Investigator. The Sponsor or its designee has the right to terminate the participation of either an individual site or the study at any time, for any reason which may include the following:

- The incidence and severity of AEs in this or other studies indicates a potential health hazard to patients.
- Patient enrollment is unsatisfactory.
- Data recording is inaccurate or incomplete.
- Investigator(s) do(es) not adhere to the protocol or applicable regulatory guidelines in conducting this study.

- Submission of knowingly false information from the study site to the Sponsor or its designee, or regulatory authorities.

In the event that the study is terminated early, the Sponsor or its designee will provide specific guidance to investigational sites regarding the end-of-study procedures.

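### Half of the named data monitoring committee is a study investigator, and investigators also decide which SAEs are recorded, so the committee gives no safety review independent of the investigators

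*Protocol*

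**What the plan says.** Protocol section 12.2 is one sentence: "The data monitoring committee will include one study investigator paired with one scientist who is not an investigator in this trial". It names no further member, chair, remit or decision rule.

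The handling of serious events is set out in section 9. Section 9.3 states: "SAEs will be assessed by the PI. Only SAEs determined by the Investigator to be possibly related or related to study procedures will be recorded". Section 9.3.1 gives the causality decision to the same role: "For each SAE the Investigator must determine whether, based on available evidence, there is a reasonable possibility that the study procedure caused the event". Section 9.1, in defining a procedure-related event, allows for a second judge; such an event is one "considered by the Investigator or the Medical Monitor (or designee) to be related to a research procedure". Section 9.4.1 sets the route outwards: "All SAEs related or possibly related to study procedures must be reported to the IRB or designee within 24 hours".

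On termination, section 12.4.5 lists as one possible reason: "The incidence and severity of AEs in this or other studies indicates a potential health hazard to patients". On how it is decided, the section says that "this action may be taken after appropriate consultation between the Sponsor or its designee and the Investigator". The committee is not mentioned there.

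**The concern.** A data monitoring committee is useful because it can read the safety data without relying on the people who run the study. Here one of its two named seats goes to a study investigator. The study is investigator-initiated (5.3) and, by section 7.3, neither blinded nor randomized.

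Composition would matter less if the committee, or some other body, received unfiltered safety data. Section 9 provides no such route. An SAE that the Investigator classes as unrelated or unlikely related is not recorded under 9.3 and does not fall under the 24-hour IRB report in 9.4.1. At stake is whether anyone outside the investigator team would see an event that the Investigator had attributed to something else. In a study this small, a safety signal would consist of very few events, so each attribution counts.

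**Working it through.** The protocol gives no figure to reproduce on this point. The check is a count, followed by a comparison of the sections.

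1. **Composition (12.2).** Named members: 1 investigator + 1 non-investigator = 2. Investigator share = 1/2 = 50%. The non-investigator has no majority among the named members.

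2. **Path of an SAE.**
   - The event occurs and the PI assesses it (9.3).
   - The Investigator assigns one of four causality classes: not related, unlikely related, possibly related, related (9.3.1).
   - Only the last two classes are recorded (9.3). Section 11.8.3 is narrower still, since it limits recording to events linked to invasive procedures.
   - The same two classes go to the IRB within 24 hours (9.4.1).
   - No step sends anything to the data monitoring committee.

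3. **Other possible checks on the relatedness decision.**
   - The Medical Monitor appears in 9.1 only as an alternative to the Investigator. Sections 9.3 and 9.3.1 give that role no part.
   - The IRB sees events only after the decision has been made, so its routine SAE reports do not test it.
   - Study monitors verify case report forms against source documents (10.2). That may bring an unrecorded event to light, but it is not a review of causality.

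4. **Power to act.** Patients may withdraw, and the PI or Primary Care Physician may discontinue a patient (5.2.1.2). Termination involves the Sponsor, the NIH, the Investigator and regulators (12.4.5). Neither section refers to the committee.

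5. **What the committee could influence.** No interim analysis is planned (11.9) and there is no blind (7.3). An investigator member therefore reveals no allocation and affects no interim efficacy decision. Only safety review is affected.

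Steps 1 to 3 together give the result: the investigator team holds half of the named committee and also decides which SAEs enter the record. No section requires a safety review that bypasses that decision.

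**The case against.** The strongest reply is that this is a 90-day pilot without a drug, in which several bodies outside the committee have a role. Related and possibly related SAEs reach the IRB within 24 hours. Monitors check source documents, and the NIH, IRB and FDA have access or audit rights (10.1, 12.4.4). The Sponsor may terminate at any time for any reason. Voting rules are often kept in a separate charter, so their absence from the protocol is not itself a fault.

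Much of this stands, and it rules out four stronger readings that a reader might infer:

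- **That the investigator member can block a recommendation.** This assumes a majority or consensus rule. Section 12.2 states no rule, and its wording does not strictly cap membership at two. A one-to-one deadlock is possible but not written.
- **That stopping needs the investigator member's consent.** Sections 5.2.1.2 and 12.4.5 place discontinuation and termination outside the committee.
- **That all oversight rests with those who judge the events.** The IRB, Sponsor, NIH and monitors have roles, and 12.2 does not say that the committee's investigator is the PI who assesses SAEs.
- **That the scientist is independent in the full sense.** The text says only that this person is not an investigator in this trial. It does not address ties to the sponsor.

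Nor do the trial's numbers measure the flaw. One event among 20 or 18 subjects is 1/20 = 5.0% or 1/18 = 5.6%, but that describes the sample size and would be the same under any committee.

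The reply does not remove the core point. The protocol itself fixes the composition, so a charter consistent with it would still seat an investigator. The IRB route carries only events that have passed the relatedness decision.

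**Conclusion.** The point holds in a limited form. One of the two named committee members is a study investigator, and investigators also decide which SAEs are recorded and reported. The committee as written therefore should not be relied on as safety review independent of the investigators.

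This rests on the wording of 12.2, 9.3, 9.3.1 and 9.4.1 alone. It needs no assumption about voting, and does not require the committee's investigator to be the PI. It does take the two named members to be the whole committee, which is the natural reading although the text does not strictly say so.

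The consequence is modest: 18 subjects in the synopsis or 20 in section 11.2, no blind and no interim analysis. The change is still worth making, because the protocol names the committee as a safeguard and the correction is cheap.

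**What to change.** 1. **Section 12.2.** State that the non-investigator scientist makes the committee's recommendation, and that the investigator member attends only to give information and has no vote.
2. **Sections 9.3 and 9.4.1.** State that every SAE is recorded, whatever relatedness the Investigator assigns, and is sent to that scientist at the same time as any IRB report. Without this, the change to 12.2 achieves little, because the scientist would see only events already judged related or possibly related.
3. **Conforming edits.** Sections 5.1.2, 8.4, 9.1, 11.8 and 11.8.3 repeat the restriction to procedure-related events and would otherwise contradict the new text. In 9.1 the definition of an adverse event is itself tied to a study procedure, so it must be widened for the phrase every SAE to have its plain meaning.

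Cost: a few sentences, slightly more reporting work and no additional staff. The drawback is that the committee's recommendation then rests on one person.

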### **12.3 Changes to the Conduct of the Study or Protocol**

Any changes in the study protocol, such as changes in the study design, objectives or endpoints, inclusion and exclusion criteria, and/or procedures (except to eliminate an immediate hazard) will be implemented only after the mutual agreement of the Investigator, IRB, and NIH or its designee. All protocol changes must be documented in protocol amendment(s). Protocol amendment(s) must be signed by the Investigator and approved by the Institutional Review Board (IRB) or Independent Ethics Committee (IEC) prior to implementation. Any changes in study conduct that result from a pending amendment will be considered protocol deviations until IRB or IEC approval is granted. Documentation of IRB or IEC approval must be returned to the Sponsor or its designee.

### **12.4 Investigator’s Responsibilities**

- ▶ The investigator will comply to guidelines provided in the following documents: Good Clinical Practice (GCP) Guidelines (ICH-E6) and the Title 45 Code of Federal Regulations (CFR) Part 46 in addition to central IRB guidelines.

#### **12.4.1 Patient Informed Consent**

Investigators must adhere to GCP, which includes ethical principles that have their origin in the Declaration of Helsinki, when developing the patient informed consent form and when obtaining consent from the patient. Written informed consent is required prior to enrollment in the study. It is the responsibility of the Investigator to document the consent process within the source documents and obtain consent using an IRB or IEC approved consent form.

The subject (20 years of age), is willing to provide written, informed consent. Confidentiality will be maintained during the study. Data and information collected during this study, including information on subject's race and ethnicity, are required by government regulatory authorities and may be published but will not include any personal identity. The study will use unique study identifiers to maintain confidentiality. Any study-related records that identify patients will be kept confidential, and to the extent permitted by applicable laws and/or regulations will not be made publicly available. Any results that are published from this study will not include a patient's personal identity.

#### **12.4.2 Case Report Forms**

Copies of pertinent records in connection with the study, including all source documents, will be made available to the Sponsor or its designee on request with due precaution towards protecting the privacy of the patient.

Data will be entered by the site into the eCRFs in the EDC system. Unless explicitly directed, blank data fields are not acceptable. Any erroneous entries made in the eCRFs must be corrected. Changes made to the data after initial entry into the eCRF will be captured via an electronic audit trail, and include the reason for change. Incomplete entries or entries needing additional explanation will be highlighted or queried to the Investigator for clarification.

#### **12.4.3 Record Retention**

The Investigator is responsible for oversight and maintenance of the study records and patient source documents. These records must be readily available for audit or inspection.

The Investigator must retain study records for at least 2 years after completion of the clinical study. However, these documents should be retained for a longer period, if required by other applicable requirements (e.g., applicable local regulatory requirement) or by an agreement with the NIH, IRB, or its designee. The Investigator will contact the NIH, IRB, or its designee prior to any record destruction.

Patient records or other source data must be kept for the maximum period of time mandated by the hospital, institution, or private practice, but not less than 15 years.

If off-site archiving is used, all records must be retrieved and made available for review at the time of an audit or regulatory authority inspection.

#### **12.4.4 Monitoring**

A Monitor will remotely interface with and may visit the Investigator periodically for the purpose of monitoring the progress of this study in accordance with the protocol, GCP, and local regulations. A monitor, auditor, IRB and or/other regulatory authority, such as the United States Food and Drug Administration (FDA), would have access to study-related medical documents for the purposes of the study. Non-compliance with the protocol, GCP, and local regulations will be documented and corrective actions implemented, as necessary. It is the responsibility of the Investigator to be present or available for consultation during remote or on-site monitoring visits. In order to complete remote or on-site monitoring visits, all data pertaining to a patient's participation in this clinical investigation must be made available to the monitor.

At any time prior to, during, or after completion of the clinical study, an audit may be performed by the NIH or its designee or a representative of a national regulatory agency may choose to inspect a study site; this includes FDA. The FDA may inspect all records related to the study. Investigators must notify the NIH or its designee upon notification of inspection by a representative of a national regulatory agency. A Sponsor or designee representative will be available to assist in the preparation for study site inspections. All pertinent study data must be made available for verification, audit, or inspection purposes.

#### **12.4.5 Study or Site Termination**

If the NIH or its designee, the Investigator, or regulatory authorities discover any conditions during the study that indicate that the study or study site should be terminated, this action may be taken after appropriate consultation between the Sponsor or its designee and the Investigator. The Sponsor or its designee has the right to terminate the participation of either an individual site or the study at any time, for any reason which may include the following:

- The incidence and severity of AEs in this or other studies indicates a potential health hazard to patients.
- Patient enrollment is unsatisfactory.
- Data recording is inaccurate or incomplete.
- Investigator(s) do(es) not adhere to the protocol or applicable regulatory guidelines in conducting this study.

- Submission of knowingly false information from the study site to the Sponsor or its designee, or regulatory authorities.

In the event that the study is terminated early, the Sponsor or its designee will provide specific guidance to investigational sites regarding the end-of-study procedures.

#### **12.4.6 Investigational Product Control**

Not applicable.

#### **12.4.7 Disclosure of Data**

All details related to the disclosure and publication of study data will be addressed in the Investigator's study contract.

#### **11.4.9 Clinical Study Report**

Reports will be made and submitted annually.

14 APPENDIX

Figure 1. Obesity in the USA
